#### 3.3 Exclusion Criteria

**Subjects meeting any of the criteria below may not participate in the study:**

1. Psychiatric illness, social situations, or active/recent (within 30 days) history of illicit substance (e.g., cocaine, heroin) abuse that would limit compliance with study requirements (e.g., study visits, medication compliance, etc.) as determined by the Investigator.
2. Patients who have had prior multiple visits in palliative medicine clinic less than one year prior to consent.
3. History of prior allogeneic stem cell transplant or liver transplant

### **3.4 Subject Withdrawal**

Subjects MAY be withdrawn from the study for the following reasons:

- More than 8 weeks pass between the completion of ESAS and the Baseline study visit.
- Subject withdraws consent from study procedures. A subject will be removed from the trial at his/her own request. At any time during and without giving reasons, a subject may decline to participate further. The subject will not suffer any disadvantages as a result.
- If, in the Investigator's opinion, compliance with study procedures is compromised and affects the integrity of the trial.
- Death.

Subjects MAY be withdrawn from the study for the following reasons:

- The subject is unable to undergo one or more study visits.
- Use, or suspicion of use, of illicit drugs or substances (i.e., positive urine drug screening) that may, in the opinion of the Investigator, have a reasonable chance of contributing to medication non-compliance
- Developing a concurrent illness or situation that would, in the Investigator's judgment, significantly affect assessments of clinical status and trial endpoints.
- DNA from buccal swabs is not viable, and the laboratory cannot perform PGx testing. Subjects may be asked to provide additional swabs if recollection performed no later than one week prior to the Baseline study visit.

Any subject removed from the trial will remain under medical supervision per standard of care procedures until discharge or transfer is medically acceptable.

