## 2.2 Endpoints

### 2.2.1 Primary Endpoint

A binary variable will be recorded for each subject undergoing PGx testing to indicate whether or not the subject received at least one drug/dose selection or modification based on their test results at any study visit where PGx results were available.

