### 5.1.1 Schedule of Clinic Assessments

Every visit can occur during a clinic visit (in-person or utilizing virtual care) or over the phone. A subject can be assessed by a trained and delegated Palliative care provider, PharmD, study coordinator, or RN:

- Baseline (day 0) study visit should be no earlier than 2 weeks and no later than 8 weeks from the first ESAS completion.
- A total of 3 subsequent study visits and the Final visit will occur every 4 weeks ( $\pm$  1 weeks) after the Baseline visit. Additionally, non-protocol-directed visits may occur on an as-needed basis (e.g., an emergency due to uncontrolled symptoms).

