## **8. REMOVAL OF SUBJECTS FROM STUDY**

### **8.1 Off Study**

Subjects are considered Off Study after completion of the subject survey and the Final visit that occurs 4 weeks ( $\pm$  1 week) after the third completed Study Visit.

Subjects may stop their participation in this study at any time if they no longer wish to participate or if the Investigator believes this to be in the best interest of the subject. When subjects are removed from the study, the reason for study removal and the date the subject was removed should be documented. Other reasons a subject may be removed from study include, but are not limited to:

- Subject non-compliance with study participation, in the opinion of the Investigator
- The subject or legal representative withdraws study consent
- The subject's tumor is confirmed to be a benign per provider
- Buccal swab collected and shipped more than 96 hours after receiving the buccal swab kit or if otherwise deemed non-viable
- The subject unwilling to recollect the buccal swabs if DNA from the first buccal swabs is not viable
- The subject is lost to follow-up
- Investigator's decision to withdraw the subject
- Subject death

Subjects that are Off Study will not participate in any study- related procedures, including data collection.

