## **11.3 Analysis Populations**

Analyses of the primary objectives and secondary objectives concerning counts of PGx-guided drug/dose selections or modifications based on their test results will be conducted on the evaluable population, defined as the population of enrolled subjects with confirmed malignancy (per provider documentation) and completing at least one study visit where PGx results are available (including the baseline visit).

Analyses of secondary objectives concerning the impact of PGx on pain and depression scores will be conducted on the primary evaluable population with valid pain and/or depression scores for at least one post-Baseline Study visit.

Analyses of secondary objectives concerning health care utilizations, costs, and subject survey responses and all exploratory objectives will be conducted on all enrolled subjects.

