### 11.4.5 Secondary Analysis

Total counts and descriptive statistics of the number of drug/dose selection/modifications made due to subject PGx test results at all visits where PGx results are available will be summarized.

A single-arm analysis for the PGx cohort will be performed: Descriptive statistics of ESAS pain scores and PHQ-9 depression scores will be calculated and summarized at study visits. Repeated-measures linear mixed models will be estimated for pain and depression, separately, adjusted for baseline clinicodemographic characteristics and include a main effect for time and a random effect for subject.

The following analysis will be performed for both the PGx and control cohorts:

A matched analysis for ESAS pain and depression scores will be carried out, comparing the study cohort to a matched cohort of unique patients receiving clinical management alone during the same time period the trial is enrolling. Standard-of-care patients with ESAS pain  $\geq 4$  and/or depression scores  $\geq 3$  at their first visit to the palliative medicine clinic or a re-establishment of care visit with the last visit being at least 1 year prior—these visits occurring within the same time period the trial is enrolling—will be identified and considered in the matched analysis.

Enrolled subjects will be matched to a similar case in cohort by:

- ESAS pain and depression symptom scores at first visit to palliative medicine clinic (i.e., study screening for study cohort)
- Age
- Sex
- Race
- Clinic visit schedule.

Between-group comparisons of those study subjects and control patients will be performed estimating repeated-measures linear mixed models for pain and depression, separately, to estimate the effect of PGx testing (i.e., treatment effect) on symptom scores adjusted for baseline clinicodemographic characteristics, a main effect for treatment, for time, an effect for treatment by time interaction, and a random effect for subject.

Additionally, the average post-baseline symptom score will be calculated for each individual (separately for pain and depression). The distributions of the average post-baseline symptom scores will be compared between the cohorts using analysis of variance techniques with adjustments for clinicodemographic characteristics.

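### If used, the option to withdraw a subject after one missed study visit ends data collection, pulls the primary proportion down, and truncates PGx follow-up by a rule controls do not have

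*Combined protocol and SAP*

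**What the plan says.** Section 3.4 has two lists of withdrawal reasons, both with the same permissive lead-in. The second includes: "The subject is unable to undergo one or more study visits". Section 8.1 states that subjects who are Off Study "will not participate in any study- related procedures, including data collection".

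Section 5.1.1 sets the follow-up: "A total of 3 subsequent study visits and the Final visit will occur every 4 weeks" after Baseline. It also makes attendance easier: "Every visit can occur during a clinic visit (in-person or utilizing virtual care) or over the phone". Section 5.1.3 lists reasons for missing ESAS, PHQ9 and survey data, including that the subject felt too ill or that staff judged the subject too ill. It does not link these reasons to withdrawal.

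The primary endpoint (Section 2.2.1) counts a PGx-based drug or dose change "at any study visit where PGx results were available". Under Section 11.3, a subject with confirmed malignancy is evaluable after "completing at least one study visit where PGx results are available (including the baseline visit"). The symptom analyses use evaluable subjects "with valid pain and/or depression scores for at least one post-Baseline Study visit".

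Section 11.4.5 compares ESAS scores with "a matched cohort of unique patients receiving clinical management alone during the same time period the trial is enrolling". Section 5 says these controls' data will be collected under a requested waiver of consent. No withdrawal rule is stated for them. The planned analyses are mixed models with a random subject effect and a comparison of each person's average post-baseline score. No sensitivity analysis is stated for dropout in the symptom scores.

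**The concern.** In a palliative clinic, a patient unable to complete a visit may well be one whose symptoms are worsening; the missing-data codes in Section 5.1.3 show that the plan expects illness to cause gaps. Sections 3.4 and 8.1 together allow one such gap to become the loss of every later observation. Much of that loss is avoidable. ESAS is routine at palliative clinic visits (Section 5.1.2), medication can be changed outside scheduled visits (Section 5.1), use of PGx results is to be documented between visits (Section 6.1, footnote 12), and removed subjects stay under standard care (Section 3.4).

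Two results are exposed. The primary proportion needs follow-up time for events to occur, and Section 11.3 keeps early leavers in the denominator. The symptom comparison sets PGx subjects, who can be removed for a missed visit, against record-based controls, who cannot. The study is unblinded (Section 4.1) and no criteria guide the use of the discretion.

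**Working it through.** **The plan's own figures.** With 65 evaluable subjects, the exact 95% Clopper-Pearson width is largest at 32 events, at 25.33%, which agrees with the stated 25% limit to rounding. Enrolment: 65 / (1 − 15/80) = 80, as stated. The half-width of 25.33/2 ≈ 12.7 points is the yardstick below.

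**How many subjects become removable.** There are four post-Baseline visits (three plus Final). If each is missed with probability p, the share missing at least one is 1 − (1 − p)^4. The documents give no miss rate, so p is assumed:

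- p = 5%: 1 − 0.95^4 = 19%
- p = 10%: 1 − 0.90^4 = 34%
- p = 15%: 1 − 0.85^4 = 48%

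These subjects are removable, not removed.

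**Effect on the primary proportion.** There are up to five visits at which a change can count (Baseline, three visits, Final). Let P be the rate with full follow-up, P1 the rate reached by the end of Baseline, and w the share removed after Baseline. All three are assumptions.

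Estimate = (1 − w)P + wP1, so bias = −w(P − P1).

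With P = 50% and a constant per-visit chance h, h = 1 − 0.5^(1/5) = 0.129, so P1 = 12.9%.

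| w | Estimate | Bias (points) |
|---|---|---|
| 10% | 0.9 × 50 + 0.1 × 12.9 = 46.3% | −3.7 |
| 20% | 0.8 × 50 + 0.2 × 12.9 = 42.6% | −7.4 |
| 30% | 0.7 × 50 + 0.3 × 12.9 = 38.9% | −11.1 |

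Over the same range of w, the bias is −2.3 to −6.9 points at P = 30% and −4.9 to −14.6 at P = 70%. If removal comes after two visits instead of one (P = 50%), it is −2.6, −5.2 and −7.7. If half of all first changes happen at Baseline (P1 = 25%), it is −w × 25, or −2.5, −5.0 and −7.5. Enrolling until 65 are evaluable does not help, because these subjects already count as evaluable.

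**Effect on the symptom comparison.** This was simulated on assumed inputs: no treatment effect, pain SD 2 between and 1.5 within subjects, about 14% of post-Baseline visits missed, and a missingness log-odds slope of 0.2 per pain point. Removing a subject at the first missed visit cut observed visits from 86% to 70%.

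| PGx final-visit mean | Only the visit lost | Subject removed | Shift due to rule |
|---|---|---|---|
| Raw observed mean | 4.81 | 4.50 | −0.31 |
| Random-intercept mixed model | 4.89 | 4.81 | −0.08 |

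Slopes of 0.3 to 0.6 gave mixed-model shifts of about 0.11 to 0.17. With the rule applied to 25% of subjects at slope 0.2, the shift was about 0.03. A separate two-arm simulation, with equal missingness in both arms and removal in PGx only, gave −0.34 on raw means and −0.13 (SE 0.02) in the mixed model; without the rule both were about zero. Overall, the planned type of model leaves roughly 0.05 to 0.2 points if every missed visit leads to removal. The result moves toward the upper end, and can pass it when missingness depends very strongly on pain, if subjects with no post-Baseline score are dropped, as Section 11.3 requires.

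**The case against.** The strongest reply is that the ground is permissive and speaks of inability, not of any missed appointment. Visits may be remote, have a window of ±1 week, and can be run by several kinds of staff. Sections 6.1, 7.4 and 8.1 time the Final visit from the third completed study visit, which suggests that gaps are tolerated. All of this stands: the figures above are conditional on use of the discretion, and full enforcement is an upper bound.

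A reader might infer more than the documents support:

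- **That the sickest subjects leave the primary and symptom analyses.** Section 11.3 keeps anyone with confirmed malignancy and one visit with results in the primary analysis, and any such subject with one valid post-Baseline score in the symptom analysis. In the primary analysis the usual problem is truncation. Only those removed before any post-Baseline score drop out of the symptom analysis.
- **That all data collection stops.** Section 11.4.5 draws billing data after closure for PGx-tested subjects and matched controls, with no exception for withdrawn subjects. This sits awkwardly with Section 8.1, and the two must be reconciled.
- **That controls stay fully followed.** Their ESAS scores exist only if they attend, so controls too ill to come also go unobserved, and matching includes visit schedule. The net direction and size in practice are therefore unknown.
- **That the raw gap of about 0.3 points is the expected bias.** The planned mixed model removes much of it. The comparison of average post-baseline scores does not model dropout.

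It is also fair to say that results are intended before Baseline, so changes may cluster there and shrink the primary bias. The P1 = 25% case shows that the bias gets smaller but does not vanish.

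**Conclusion.** The concern holds as a conditional, avoidable bias. One stated rule allows a missed visit to end study follow-up, another section treats the same situation as missing data, and controls have no counterpart rule.

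For the primary proportion the direction is clear: downward relative to full follow-up, whenever a removed subject would later have had a first PGx-guided change. The size is about 4, 7 or 11 points for 10%, 20% or 30% removed after Baseline, given a 50% rate and a constant per-visit chance. The largest of these approaches the planned half-width of about 12.7 points. Neither the removal rate nor the timing of changes is given in the documents.

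For the symptom comparison the effect is small: roughly 0.05 to 0.2 ESAS points under the planned mixed model with every missed visit enforced, and less with partial use. It tends to favour PGx if missed visits track worse symptoms, which is plausible but not stated. This is worth correcting because the change is cheap, not because the comparison is shown to be badly distorted.

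**What to change.** 1. In Section 3.4, delete the missed-visit ground. Record the visit as missed with a reason, consistent with Section 5.1.3.
2. In Section 8.1, separate stopping study visits from stopping data collection. For subjects who have not withdrawn permission to use their records, continue to abstract chart ESAS, medication changes with PGx use, and encounters up to the planned Final date, on the same basis as for controls.
3. In Sections 2.2.1, 11.3, 11.4.4 and 11.4.5, state that these chart data enter the primary and symptom analyses, including changes recorded after study visits have stopped.
4. Reconcile Section 8.1 with the billing-data collection in Section 11.4.5.

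The cost is a protocol amendment, possibly a consent amendment, and a small amount of extra chart abstraction. The limit of the fix is that chart ESAS is recovered only for patients who return to clinic, so some illness-related gaps will remain in both cohorts.

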### **3.5 Screen Failures**

A subject who, for any reason (e.g., failure to satisfy the eligibility criteria or withdraws consent), terminates his/her study participation before being enrolled to the study is regarded as a screen failure. All screen failures will be tracked. Reasons for screen failure (e.g., specific inclusion/exclusion criteria not met) will be recorded in the CTMS/Subject Console.

## **4. REGISTRATION**

### **4.1 Sequence Number Assignment**

Following informed consent, subjects will be registered by the LCI Data Coordinating Center and assigned a Sequence Number.

The study intervention (PGx testing) is not blinded to the subject or the Investigator.

## **5. STUDY PLAN**

The study design is a prospective interventional clinical trial designed to investigate the application of PGx testing to personalize cancer symptom management, particularly pain and depression.

Potential candidates will be presented with consent; screening data for these patients, including ESAS symptom scores, will be captured and used for analysis ([Section 11.4.5](#)). A full waiver of consent and HIPAA for data collection will be requested for the control cohort, which includes patients (with pain  $\geq 4/10$  and/or depression  $\geq 3/10$  who have not been presented with consent and who were presented with consent but decline participation in the study (i.e., do not consent). Study subjects who consent and subsequently screen fail for any reason will also be included in the control cohort. Patients who agree will undergo the informed consent process, and subjects who consent will be screened for eligibility. Those meeting eligibility criteria will be enrolled and undergo buccal swab collection. **Enrollment day** will be considered at the **buccal swabs collection day**. If the collected buccal swabs do not contain enough viable DNA for PGx testing, subjects may be asked to provide additional swabs. No less than 2 weeks and no more than 8 weeks should pass between the first ESAS completion and the date of the **Baseline study visit**. **The Baseline study visit** may be completed during a clinic visit (in person or virtually) or over the phone. It is estimated that PGx results will be available within five business days of swab receipt by the laboratory, and a detailed report will be sent to the clinic. A copy of the test results in PDF (Portable Document Format) format and PGx consultation note will be uploaded to the subject's medical chart. Apart from the availability and use of PGx test results to guide pharmacotherapy, subjects will receive standard of care treatment and undergo ESAS screening during the palliative medicine visits. PHQ9 will be collected by the research team electronically, during the study visit by paper, or by phone. Data, including symptom scores and medications, at each visit, will be captured until the **Final study visit**. Subjects will be asked to complete a short survey within 30 days after the Final study visit to assess their perspectives on PGx testing and the care they received (administered preferably electronically, alternatively via paper during the Final visit at a clinic or over the phone).

Subjects presenting with depression score 3 or greater and/or experiencing depressive symptoms during the clinical trial are highly encouraged to receive treatment in the LCI psycho-oncology clinic.

Subjects will be offered the option to complete study visits during a clinic visit (in-person or virtually) or over the phone.

Subjects will not be reimbursed for study participation; however, they will receive PGx testing at no cost and will receive a full copy of their test results at their request.

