Research team will collect PHQ9 prior to the study visit, preferably electronically or by phone, within 2 business days and send them to the Supportive Oncology provider and Sponsor-Investigator. If the response for the PHQ9 question #9 is anything greater than 0, a research designee will contact the applicable LCI social worker. Alternatively, PHQ9 can be collected during clinic visits on paper.

ESAS will be obtained during a clinic visit or utilizing virtual care.

ESAS score done historically visit per standard of care at the initial palliative medicine visit will be collected in the dataset and used for analysis ([Section 11.4.5](#))

Medications listed in [Appendix D](#), currently taken and/or newly prescribed during the visit, and other drugs and/or drug modifications recommended by the pharmacist or provider based on PGx test results outside those in [Appendix D](#) list will be collected every study visit.

Use of PGx test results should be documented any time a drug/dose modification is made (during palliative medicine visits or in between visits).

HCRU (defined as any encounter classified as an outpatient (OP), inpatient (IP), or emergency department (ED) encounter) occurring during the study period will be collected by a research designee. Each encounter will be counted as unique per classification. IP encounters that result from an emergency department presentation will be classified as both an ED encounter and IP encounter. Any encounter lasting longer than 24 hours will be considered an IP encounter. Insurance status and/or type and reason for presentation at each encounter will also be collected.

Survey will be preferably administered electronically (distributed to the subject's email within 30 days after the Final visit). Alternatively, a research designee can collect a survey via paper during the Final visit at the clinic (or sooner if withdrawn) or over the phone as an option.

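### The matched comparison in Section 11.4.5 cannot attribute a symptom difference, mainly in ESAS depression, to PGx testing alone, because study subjects also receive research-driven depression steps not described for controls

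*Combined protocol and SAP*

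**What the plan says.** Section 5 presents PGx results as the one departure from usual care: "Apart from the availability and use of PGx test results to guide pharmacotherapy, subjects will receive standard of care treatment". The same section then says that subjects with a depression score of 3 or more, or with depressive symptoms during the trial, "are highly encouraged to receive treatment in the LCI psycho-oncology clinic".

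Table 2 schedules PHQ9 at Baseline, three study visits and the Final visit. Under footnote 8 the research team obtains the scores and must "send them to the Supportive Oncology provider and Sponsor-Investigator". If item 9 is above 0, "a research designee will contact the applicable LCI social worker".

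Section 11.4.5 describes the comparator as a "matched cohort of unique patients receiving clinical management alone during the same time period the trial is enrolling". On the control data, Section 5 says: "A full waiver of consent and HIPAA for data collection will be requested for the control cohort". Matching uses first-visit ESAS pain and depression scores, age, sex, race and clinic visit schedule. The outcomes are ESAS pain and ESAS depression. The mixed model adjusts for baseline characteristics and is fitted "to estimate the effect of PGx testing (i.e., treatment effect) on symptom scores".

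**The concern.** Feeding depression scores back to the treating provider, contacting a social worker and steering patients to psycho-oncology can each lower a depression score without any genotype being used. If they reach one cohort more than the other, the treatment term in the model absorbs their effect. Section 11.4.5 nevertheless names that term the effect of PGx testing. No planned table, sensitivity analysis or stated limitation for the symptom comparison deals with this; the sensitivity analyses mentioned in 11.4.5 sit in the utilization and cost paragraph.

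What is at stake is the interpretation of a secondary result. A lower ESAS depression score in the PGx cohort could be reported as evidence for PGx-guided prescribing when the design cannot separate it from the added depression care. Any effect on ESAS pain would be indirect.

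**Working it through.** **Step 1. What differs between the cohorts after the first visit**

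| Element | PGx cohort | Controls | Balanced by matching or baseline adjustment? |
|---|---|---|---|
| PHQ9 collected and sent to the provider | Research team, around 1 + 3 + 1 = 5 visits (Table 2, footnote 8) | None described; data collection under a waiver | No |
| Social-work contact if item 9 is above 0 | Research designee (footnote 8) | None described | No |
| Psycho-oncology encouragement | Stated (Section 5) | Not stated either way | No, if it differs |
| Visit contact | Every 4 weeks (5.1.1), possibly by phone | Usual palliative visits, with routine ESAS | Partly, through clinic visit schedule |
| Pharmacist counselling on results | Stated (1.2, 10.1.3) | Not applicable | Not needed: part of the PGx intervention |

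The first two rows are research-team actions, and the point stands on them alone. The third is a possible difference. If its threshold of 3 is read as an ESAS score, it equals the ESAS depression entry threshold in Section 3.2, so every subject entering on that score meets it.

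**Step 2. The plan's own figures**

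The documents give no alpha, power, effect size or standard deviation for the matched comparison, so there is no figure to reproduce for it. The only precision statement (11.2) concerns the primary proportion. With 65 evaluable subjects the largest exact Clopper-Pearson width is 25.3%, which matches the stated 25% to the nearest whole percent. It has no bearing on this point.

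**Step 3. Illustration of size; all inputs assumed**

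Assume no true PGx effect, 1:1 matching with 65 per cohort (the plan states no ratio), and two-sided alpha 0.05. Let *u* be the excess share of PGx subjects receiving additional depression care, 0.10 to 0.40. Let *e* be the effect of that care, 0.3 to 0.8 SD of the ESAS depression outcome.

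- Spurious difference: *b* = *u* × *e*
- Standard error in SD units: √(2/65) = 0.175
- Chance of a significant result: Φ(*b*/SE − 1.96) + Φ(−*b*/SE − 1.96)

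| *u* | *e* | *b* (SD) | *b*/SE | Chance of a false PGx effect |
|---|---|---|---|---|
| 0.10 | 0.3 | 0.03 | 0.17 | 5.3% |
| 0.30 | 0.5 | 0.15 | 0.86 | 13.7% |
| 0.40 | 0.8 | 0.32 | 1.82 | 44.6% |

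With 50 per cohort the range is 5.3% to 36.0%. For scale, the difference detectable with 80% power at 65 per cohort is (1.960 + 0.842) × 0.175 = 0.49 SD. This is a two-sample approximation to the planned mixed model, and it shows only that the answer depends on uptake, which the plan does not say it will compare between cohorts.

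**The case against.** The strongest reply is that much of the extra care may be usual care. Section 10.1 classes all supportive treatments as standard of care. Psycho-oncology is an existing clinic, and controls attend the same palliative service over the same period with similar first-visit scores. The Section 5 sentence speaks of treatment, and the same paragraph openly says that the research team collects PHQ9. Item-9 contact is a safety step that reaches only those scoring above 0. The comparison is non-randomised and secondary.

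Much of this stands, and it rules out several stronger readings:

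- A reader might infer that controls are not steered to psycho-oncology. The documents do not say so; the encouragement is written for trial subjects, and usual-care practice is left unstated.
- A reader might infer that scheduled contact reaches no controls. Controls have palliative visits, and matching on clinic visit schedule is aimed at this. How well it works is unknown, since study visits may be by phone.
- A reader might count pharmacist counselling as a separate co-intervention. Sections 1.2, 5.1 and 10.1.3 tie the pharmacist's role to interpreting and explaining the test results.
- A reader might infer a large bias. Nothing in the documents fixes its size.

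The reply does not answer the PHQ9 routing and item-9 contact. These are research-team steps with no described counterpart in controls, and adjustment for baseline characteristics cannot remove care given later.

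**Conclusion.** The label in Section 11.4.5 claims more than the design can isolate. The between-cohort difference estimates the effect of PGx testing together with study PHQ9 feedback, item-9 social-work contact and possibly more psycho-oncology encouragement, compared with usual management. This applies mainly to ESAS depression.

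The likely direction favours PGx. The bias could be negligible or material: 0.03 to 0.32 SD under the assumed uptake and effect ranges, none of which comes from the documents. The conclusion rests on reading the absence of any described PHQ9 routing or item-9 contact for controls as absence of those steps, which fits data collection under a waiver.

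This should be corrected, but it does not threaten the trial's main result. The primary endpoint is a single-arm proportion and is untouched.

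**What to change.** No patient care changes.

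1. In 11.4.5, replace the phrase that equates the treatment effect with PGx testing. Suggested wording: *to estimate the effect on symptom scores of the PGx study programme (PGx testing with pharmacist input, plus study PHQ9 feedback, item-9 social-work contact and any psycho-oncology encouragement) versus usual clinical management*. Align the secondary objective in 2.1.2 and the synopsis.
2. From the data-warehouse diagnosis and procedure codes that 11.4.5 already plans for both cohorts, tabulate by cohort over the same follow-up window the number and share with a psycho-oncology or social-work encounter, and the number of palliative visits. Do this as far as the codes identify them, and note that unbilled contacts may be missed. Keep the table descriptive. Do not adjust for these encounters in the main model, because post-baseline care may itself respond to PGx-guided treatment. State that a depression difference will not be attributed to PGx-guided prescribing alone.
3. Reconcile the Section 5 sentence on standard care with the psycho-oncology sentence in that section and with Table 2, footnote 8.

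The cost is a few lines of text, one extra table and a more modest claim. Whether the codes can identify the relevant clinics should be checked before the table is promised.
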